#### Central independent blinded photographic reviewer and volumetric change measurement

A central independent blinded photographic reviewer (see section 6.4.13) and staff at the photo provider conducting the volume changes measurement (see section 6.4.12) will:

- be dislocated from the investigation sites
- will have no access to randomization schedule / eCRF or information on treatment assignment, and
- will not discuss any findings with the treating investigators and blinded evaluators at the sites during the investigation until after the final study database lock.

#### Emergency unblinding

There will be no special procedure for emergency unblinding because the treating investigator and other study staff will be aware of the treatment allocation. In case, only the blinded evaluator at the site is available in case of an emergency situation, and an unblinding is required, he/she **should** contact the Medical Monitor or the Sponsor first before accessing the subject's medical records for unblinding.

The subjects will know that they have received a hyaluronic acid dermal filler with lidocaine, which is, sufficient level of information needed in case of emergency. However, the subjects will receive a participant card with 24/7 emergency telephone numbers.

Any cases of unblinding will be documented by the site staff.

#### 6.1.4 Discussion of clinical investigation design

This clinical investigation is undertaken to evaluate the effectiveness, safety and long-term safety of saypha® VOLUME Lidocaine for the correction of moderate to severe midface volume deficit, and to demonstrate its non-inferiority to one of the devices approved for the same indication

after implantation will be assessed.

The investigation is designed to minimize potential bias during collection of clinical observations and to allow for interpretation of results in the context of available treatment options.

Approximately 486 subjects will be randomized in this investigation (324 test device and 162 comparator device) in order to get a sufficient number of evaluable subjects per treatment group (437 in total). The sample size selection is justified in section 7.1. The method of randomization is used to minimize the bias arising from the assignment of subjects to treatment groups (see section 6.1.2).

The primary and several secondary and other effectiveness endpoints (see section 5.3) are based on the 5-grade MVDSS, a validated instrument for semi-quantitative assessment of volume deficit in the midface as assessed live by the blinded evaluator at the site.[33] Blinded outcome assessment by a blinded rater is a common practice to reduce bias arising from the expectations of individuals collecting data. The sites will make their best efforts to assign the same blinded evaluator for evaluation activity throughout the clinical investigation to maintain consistency of effectiveness evaluation (see section 6.4.12).

In view of multicenter conduct of the investigation, the validated MVDSS assessment will be also evaluated centrally, by experienced independent blinded photographic reviewers.[34] This will allow for unified assessment of treatment responses across the sites and checking if any bias was introduced by inter-observer variability between the sites.

The rater blinding regarding treatment group in initial treatment will remain in effect until study data base lock. The blinded evaluator at the site will be trained on the MVDSS and NLF-SRS prior to start of the investigation during the investigator meeting, a live WebEx with a sponsor medical consultant, or through review of a recording of the WebEx. Open questions by on-site located raters will be answered during the pre-study visits; further training on the scale will be also performed during site pre-study visits, if needed. The independent blinded photographic reviewers will be trained on the MVDSS prior to their assessments of the photographs.

In addition, the improvement of midface volume deficit will also be evaluated centrally by using computerized volume change measurement based on the 3D photographic images. The quantified data of the volume change measurement provide additional evidence confirming the effectiveness of the test device for the indication to be treated (see section 6.4.12).

The time point for definition of the primary endpoint (Week 24 after last injection of the initial treatment phase) was selected based on clinical experience with other HA fillers and will be corroborated by earlier and later observations (see Table 1 and Table 3 for details). Difference of one grade on this scale is considered to be clinically meaningful since it can be visually recognized by various observers as demonstrated during validation of the scale.

The clinical relevance of the investigation will be also supported by several (other) secondary effectiveness endpoints (see section 5.3), related to global aesthetic improvement (by using the modified GAIS) [35] and subject's satisfaction with outcome (overall and the cheeks by using FACE-QTM scales).[36, 37]

Information on occurrence of pain will be primarily obtained by collection of AEs, with additional insight into pain intensity being obtained directly after the injection using a semi-quantitative 11-point Numeric Pain Rating Scale (NRPS).[38].

Touch-up treatments are allowed in the investigation, and the treating investigator will determine the appropriate injection volume and injection technique and equipment (i.e., needle/cannula) based on his/her clinical experience (see sections 6.2). A minimum of 100 subjects randomized to the test device will be treated with either needle or cannula. Use of either needle or cannula is based on the treating investigator's medical decision.

Finally, it is well known that in routine clinical practice many patients choose for repeating treatments with HA dermal fillers to maintain the aesthetic improvement achieved with the first one.[39-41] A repeat-treatment at one of the later time points (earliest Week 48 after baseline treatment) has been therefore added, not only to improve subject retention in the investigation, but also to collect safety data after repeated administration of the test device. This actually allows the sponsor to determine if subjects previously treated with a different device behave differently with exposure to saypha® VOLUME Lidocaine.

Safety and long-term safety of saypha® VOLUME Lidocaine for the correction of moderate to severe midface volume deficit will be monitored by documentation of safety parameters (AEs, injection site reactions and device deficiencies; see section 6.4.19).

Overall, the proposed design for this investigation is considered ethically and scientifically justified.

# 6.2 Handling and Administration of the medical devices

A description of both devices is given in section 2.

## 6.2.1 *Packaging, labelling and storage*

## Labelling and traceability of the devices

The study labels will comply with appropriate information as mandated by applicable guidelines and national regulatory requirements, as appropriate.

Label text will be available into local languages and a copy will be filed in the TMF.

Study labels will include the batch number (lot number) and a kit number. Both devices are identified and tracked by those batch numbers. To ensure the traceability of each device, the batch numbers must be documented in the source medical record of the subject treated with the device.

	Saypha® VOLUME Lidocaine	
Packaging	Per carton box (= one kit)	Per carton box (= one kit)
	
 
One prefilled syringe of 1.0 mL filler solution
 
two 27G /2" disposable sterile needles
 
	
 
Two prefilled syringes of 1.0 mL filler solution, each
 
four 27G /2" disposable sterile needles
 

		Note: The volume in each syringe is as stated on the syringe label and on the carton.
Optional / additional	25G 1½" cannula	25G 1½" cannula
injection equipment	Note: Cannulas will be provided by the sponsor's representative.	
Batch number	Batch number will be on the study label	Batch number will be on the study label
Kit number	Kit number will be on the study label.	Kit number will be on the study label
Storage	Store at + 2 to + 25 °C/ +36 to +77 °F in a dry place in the original box and protected from light, heat and frost.	Store at room temperature (up to 25°C/77°F). DO NOT FREEZE.
	Finished sterilized saypha® VOLUME Lidocaine product has a shelf life of 36 months at 2 to 25°C.	must be used prior to the expiration date printed on the label.
Note: The safety and en	fectiveness of cannula injection of 25G 1½" cannulas	has only been clinically evaluated
Note: may be injected with a 25G 1" needle according to the IFU. However, use of needles other than 27G  / 2 " is not allowed within this clinical investigation.		

**Table 14.** Storage and packaging of the devices.

# 6.2.2 Administration (test and comparator devices)

# Anatomic areas of midface treatment

The anatomic areas of midface treatment are defined as follows:

- Anteromedial cheek (left and right)
- Submalar (left and right)
- Zygomaticomalar (left and right)

A visual depiction of the anatomic areas of midface treatment is given in Figure 3.

# Figure 3. Anatomic areas treated.

Antero- medial cheek Submalar	

		• The injection technique for regard to the angle and orientation of the bevel, the depth (subcutaneous and/or submuscular/ supraperiosteal) of injection, and the quantity administered may vary depending on the area being treated. Injection of the filler too superficially (intradermally), or in large volumes over a small area, may result in visible and persistent lumps and/or discoloration.	
Injection equipment	Either needle or cannula will be used (see below) in the discretion of the treating investigator. A minimum of 100 subjects randomized to the test device will be treated with either needle or cannula.		
	• 27G ½" needle (provided with the syringe)	• 27G ½" needle (provided with the syringe)	

provided separately)

Table 15. Description of injection technique and injection equipment used in the investigation

25G 1 1/2" cannula

provided separately)

25G 1/2" cannula

# Administration of saypha® VOLUME Lidocaine and

Table 16 gives detailed instructions how to administer the test device and the comparator device.

## Table 16. Administration of saypha® VOLUME Lidocaine and

Step	saypha® VOLUME Lidocaine [also see current version of IB]	[also see IFU] [14]		
Prior to administration	The device must be injected into non-inflamed, disinfected, healthy skin			
	• After ensuring that the subject has thoroughly washed the treatment area with soap and water, the area should be prepped with alcohol or another antiseptic.			
	ote: IB for saypha® VOLUME Lidocaine (section 8.1.5 therein) and IFU for an and the say for the saypha® VOLUME Lidocaine (section 8.1.5 therein) and IFU for an			
	Whenever possible (i.e., if the subject agrees) additional topical anaesthetic assessment (as collected via Numerical Pain Rating Scale; see section 6.4.14).	ever possible (i.e., if the subject agrees) additional topical anaesthetic (patch or cream) should be avoided in this investigation to not falsify the pain sment (as collected via Numerical Pain Rating Scale; see section 6.4.14).		
	In case additional local anesthesia is used, this has to be documented as concor	In case additional local anesthesia is used, this has to be documented as concomitant treatment in the subject's records and the eCRF.		
Preparation for administration	Instructions incl. visual illustration how to attach needle / cannula to the syringe is given in section 20.3.	Instructions incl. visual illustration how to attach needle / cannula is given in section 20.4 and in the IFU [14]		
		Note: Failure to comply with the needle attachment instructions could result in needle disengagement and/or product leakage at the and needle hub connection. In such case follow instructions given in section 14.9.		
Administration	The following applies to saypha® VOLUME Lidocaine and	(according to IFU of [14])		
	• If the needle/cannula is blocked, do not increase the pressure on the plunge	f the needle/cannula is blocked, do not increase the pressure on the plunger rod. Instead, stop the injection and replace the needle/cannula		
	• When using a cannula, an entry point is made in the skin, e.g., with a sharp	ula, an entry point is made in the skin, e.g., with a sharp needle of appropriate size		
	After insertion of the needle, and just before injection, the plunger rod shoul	e needle, and just before injection, the plunger rod should be withdrawn slightly to aspirate and verify the needle is not intravascular.		
	
 
After the first small amount of material has been injected into the patient, wa rest of the injection.
 
	nount of material has been injected into the patient, wait a full 3 seconds to allow the lidocaine to take effect before proceeding with the		
	• Distribute in small aliquots (small boluses of 0.1 mL to 0.2 mL) over a large	liquots (small boluses of 0.1 mL to 0.2 mL) over a large area to reduce the risk of persistent lumpiness.		
	With submuscular/supraperiosteal injection, the number of times the needle passes through the muscle should be minimized to reduce the risk of bruising is important to stop injecting before the needle tip reaches the level of the deep dermis to prevent material from being placed too superficially in the skin.			

сгота

CONFIDENTIAL

Table 16. Administration of saypha® VOLUME Lidocaine and

Step	saypha® VOLUME Lidocaine [also see current version of IB]	[also see IFU] [14]
	
 
Correct to 100% of the desired volume effect. Do not overcorrect. The degree and duration of the correction depend on the character of the defect treated the tissue stress at the implant site, the depth of the implant in the tissue, and the injection technique. Markedly indurated defects may be difficult to correct of limit in the injection should be stopped, and the area massaged until it returns to a normal color. Blanching may represent a vesse occlusion. If normal skin coloring does not return, do not continue with the injection. Treat in accordance with the guidelines, which include hyaluronidase injection as given in section 6.2.5. Also see sections 6.3.6, 14.5.4 and 16.1.
 
The maximum volume to be applied per treatment and the overall investigation is given in section 6.2.3.
 
	
Completion of administration	After the injection, doctors may apply a light massage in order to distribute the product uniformly.	• The area of lost facial volume should be lifted by the end of the injection. When injection is completed, the treated site may be gently massaged to mold the product to the contour of the surrounding tissue and assure that it is evenly distributed and conforms to the contour of the surrounding tissues. If overcorrection occurs, massage the area between your fingers or against an underlying superficial bone to obtain optimal results.
After administration	
 
After use, treatment syringes and needles may be potential biohazards. Handle and dispose of these items in accordance with accepted medical and applicable local, state, and federal requirements (please also see sections 6.2.6 and 6.2.7).
 
Pain intensity will be assessed immediately after injection, and at 15 min-intervals for 60 min post-treatment by using the NPRS (see section 6.4.1 details).
 
	
	
 
In order to identify potential AEs (especially, to detect blanching caused by arterial occlusions) post-administration of device (baseline treatment, to treatment and repeat-treatment) a safety evaluation 15 minutes after the administration needs to take place (see section 6.4.19).
 
	
	
 
Should any of the vision assessments (Snellen visual acuity, confrontational visual test field, or ocular motility – see section 6.4.76.4.8) s after the injection of the device, the treating investigator must examine the subject to exclude vascular injection and contact an eye spec
 
	
	
 
A basic neurological examination (F.A.S.T) will be performed for all subject section 6.4.9).
 
	ts who show signs of ophthalmic complications due to filler injection (see
	
 
Prior to discharge the subject should be advised to follow restrictions speci any unwanted event.
 
	ified in section 6.3.8 and to inform their investigator as soon as possible about
Details for each treatment will be documented in the subject's records and the eCRF with the same level of details		the eCRF with the same level of details (see section 6.4.10).

# 6.2.3 Applied volume of the devices

The volume administered is at the discretion of the treating investigator and depends on the severity of the midface volume deficit to be corrected.

However, the maximum volume (left and right side of the midface together) must not exceed 10 mL in total per treatment phase (initial and repeat-treatment, respectively, including touch-up treatments) or 20 mL per 60 kg (130 lbs) body mass per year.

A maximum of 6.0 mL on one side of the midface is allowed total per treatment phase (i.e., a maximum of 4.0 mL on the other side).

Table 17 gives an overview of the average volume of the devices administered in the clinical investigation.

Treatment Session	saypha® VOLUME Lidocaine	
Initial treatment phase per subject (baseline treatment plus touch-up treatment)	Total volume must not exceed 10 mL per 60 kg (130 lbs) body mass in total (baseline plus touch-up treatment; left and right side of the midface together)	Total volume must not exceed 10 mL per 60 kg (130 lbs) body mass in total (baseline plus touch-up treatment; left and right side of the midface together)
Repeat-treatment phase per subject (repeat-treatment plus touch-up treatment)	Total volume must not exceed 10 mL per 60 kg (130 lbs) body mass in total (repeat-treatment plus touch-up treatment; left and right side of the midface together)	Total volume must not exceed 10 mL per 60 kg (130 lbs) body mass in total (repeat-treatment plus touch-up treatment; left and right side of the midface together)
Total volume per subject during the entire study	Total volume must not exceed 20 mL per 60 kg (130 lbs) body mass in total	Total volume must not exceed 20 mL per 60 kg (130 lbs) body mass in total

Table 17. Volume of the devices administered in the clinical investigation per treatment and overall

Note 1: 'Year' means rolling 365 days, starting with study start / baseline injection.

Note 2: Based on preclinical studies and a toxicological risk assessment, subjects should be limited to 20 mL of per 60 kg (130 lbs) body mass per year. The safety of injecting greater amounts has not

been established. [14]

However, for this investigation, the above given limit must be followed for both devices.

After each administration, the actual volume of the device injected will be recorded in the subject's source records and in the eCRF (also see section 6.4.10).

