	17.	Planned dental/oral surgery or modification (bridge-work, implants) within four weeks prior to the injection and to a minimum of four weeks post injection
	18.	Any medical condition prohibiting the inclusion for repeat-treatment according to the judgement of the treating investigator
	19.	Beard longer than three-day beard, or excessive facial hair that could interfere in evaluation of treatment as judged by the investigator

20. Previous enrollment in initial treatment phase of this clinical investigation and early termination, or significant incompliance with the protocol requirements
21. Current or previous treatment with another investigational drug and/or medical device or participation in another clinical study
22. Midface volume deficit due to a trauma, or abnormalities in facial adipose tissue distribution such as those associated with HIV related lipodystrophy
23. Subjects who experienced weight change for a minimum of 10% since study start or subjects who have the intention to change eating habits that result in a weight gain or loss >10% during the entire investigation
24. Subjects with active COVID-19 infection and subjects with symptoms consistent with COVID-19 infection including any other respiratory symptoms/illnesses within the past 14 days unless tested negative prior to Visit RT1

INVESTIGATIONAL D	EVICE(S), DOSE AND MODE OF ADMINISTRATION
Test device	saypha® VOLUME Lidocaine: Crosslinked hyaluronic acid (HA) 23 mg/mL + 0.3% lidocaine hydrochloride.
Comparator device	: Crosslinked HA 20 mg/mL + 0.3% lidocaine hydrochloride
Dose and mode of administration	The respective device will be administered by subcutaneous and/or supraperiosteal injection. The injection technique used will be selected by the treating investigator.
	For injection, either a needle (27G ½") or cannula (25G 1½") may be used in the discretion of the treating investigator. A minimum of approximately 100 subjects randomized to the test device will be treated with either needle or cannula.
	The volume administered is at the discretion of the treating investigator and depends on the severity of the midface volume deficit to be corrected.
	However, the maximum volume (left and right side of the midface together) must not exceed 10 mL in total per treatment phase (initial and repeat- treatment, respectively, including touch-up treatments) or 20 mL per 60 kg (130 lbs) body mass per year.

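### The per-phase volume limit is a flat 10 mL in the synopsis and section 6.2.3 text but is scaled to body mass in Table 17, so the two differ for subjects under 60 kg

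*Protocol*

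**What the plan says.** The synopsis (dose and mode of administration) states that the volume for both sides together "must not exceed 10 mL in total per treatment phase". The section 6.2.3 text repeats this, making clear that touch-ups count: "must not exceed 10 mL in total per treatment phase (initial and repeat-treatment, respectively, including touch-up treatments"). In both places the only weight-scaled limit is a yearly one, 20 mL per 60 kg. Section 6.2.3 adds a side limit: "A maximum of 6.0 mL on one side of the midface is allowed total per treatment phase", which leaves 4.0 mL for the other side.

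Table 17 follows in the same section. Its row for the initial phase ("baseline plus touch-up treatment; left and right side of the midface together") and its row for the repeat-treatment phase both cap the volume at 10 mL "per 60 kg (130 lbs) body mass", in both device columns. A third row, headed "Total volume per subject during the entire study", gives 20 mL on the same weight basis.

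The table is introduced with "Table 17 gives an overview of the average volume of the devices administered in the clinical investigation", although its cells state maxima. Note 1 defines a year as a rolling 365 days. Note 2 gives a toxicological basis for 20 mL per 60 kg per year. The section then says: "However, for this investigation, the above given limit must be followed for both devices".

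**The concern.** Table 16 in section 6.2.2 sends the injector to section 6.2.3 for the maximum volume. For a subject under 60 kg that section gives two different ceilings for the same phase. Nothing states which prevails. The closing sentence refers to one limit in the singular and, coming straight after Note 2, may mean only the yearly limit.

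A maximum injected volume is a safety limit and should have one reading. With two, sites may apply different ceilings. The data review meetings, which grade deviations under section 7.2 and discuss all of them under section 10, would have no fixed standard for deciding whether a given injection was a deviation.

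The cumulative limit has a related mismatch. It is per year in the synopsis, the section 6.2.3 text and Note 2, but for the whole study in Table 17.

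**Working it through.** **Inputs**

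- Flat per-phase limit: 10 mL (synopsis; section 6.2.3 text).
- Side limits: 6.0 mL and 4.0 mL (section 6.2.3 text).
- Table 17 per-phase limit: 10 mL per 60 kg, both phases.
- Yearly limit: 20 mL per 60 kg (synopsis; section 6.2.3 text and Note 2).
- Participation: up to 92 weeks (section 6.3.1).
- Body weights: assumed for illustration. The eligibility criteria set no minimum weight, so subjects under 60 kg can be enrolled.

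**Step 1. The plan's own figures.** The side limits add up to 6.0 + 4.0 = 10.0 mL, which agrees with the flat limit. Table 17's two phase rows add up to 10 + 10 = 20 mL per 60 kg, which agrees with its whole-study row. Each version is consistent within itself; the conflict is between them.

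**Step 2. Flat limit against Table 17.** The Table 17 limit is 10 × kg/60. With all limits applied together, the gap is 10 − min(10, 10 × kg/60).

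| Weight (assumed) | Text limit | Table 17 limit | Gap |
|---|---|---|---|
| 45 kg | 10 mL | 10 × 45/60 = 7.50 mL | 2.50 mL |
| 50 kg | 10 mL | 10 × 50/60 = 8.33 mL | 1.67 mL |
| 55 kg | 10 mL | 10 × 55/60 = 9.17 mL | 0.83 mL |
| 60 kg | 10 mL | 10 × 60/60 = 10.00 mL | 0 |

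Above 60 kg, Table 17 read alone would allow more than 10 mL (11.67 mL at 70 kg). The flat limit is then the tighter one, so nothing conflicts when both are applied.

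**Step 3. Which injections are affected.** A per-phase volume V of up to 10 mL meets the text but exceeds Table 17 when 10 × kg/60 < V, that is, when weight is below 6 × V kg.

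- 10 mL: below 60 kg
- 9 mL: below 54 kg
- 8 mL: below 48 kg
- 7 mL: below 42 kg

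Example: 9 mL at 50 kg exceeds Table 17 by 9 − 8.33 = 0.67 mL.

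**Step 4. Does the yearly limit settle it?** The yearly limit is 20 × kg/60, which is at least 10 mL whenever weight is at least 30 kg. At 50 kg it is 16.67 mL. At realistic adult weights it therefore never brings a single phase below the flat 10 mL. For the same reason, the toxicological basis in Note 2 does not explain the scaled per-phase rows.

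**Step 5. Time base.** Participation can last 92 × 7 = 644 days, against the 365 days of Note 1, so a yearly limit and a whole-study limit cover different periods. No separate volume gap is claimed here, because Table 17's phase rows already add up to its study row.

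**The case against.** The strongest reply is that both statements are ceilings and can be met together. Keeping to the lower figure satisfies both, so no injector is forced into a breach. The gap exists only below 60 kg and only for volumes near the ceiling. How many subjects combine the two is unknown. All of this stands, and it limits the weight of the point. It does not give the protocol a single limit, because a site that follows the text alone would be following a stated rule.

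Section 4.2.2 reports that in the comparator's pivotal study device- and injection-related adverse events were more frequent above 9 mL. That shows such volumes do occur. It says nothing about body weight or about volumes in this trial, and it should not be read as evidence for either limit.

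The wording of the lead-in and the time-base mismatch are minor beside the per-phase conflict. Which weight to use is also a smaller matter: weights are available close to treatment, and the yearly limit already depends on body mass under any reading.

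Finally, the rationale in Amendment 5 (section 19.5) suggests recruitment had finished before the current version. If so, a correction would mainly serve any repeat treatments still to be given and the classification of deviations.

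**Conclusion.** The contradiction is real and lies in the current text. The synopsis, the section 6.2.3 text and the side limits give a flat 10 mL per phase; both phase rows of Table 17 give 10 mL per 60 kg. Below 60 kg the limits differ by 0.83 mL at 55 kg, 1.67 mL at 50 kg and 2.50 mL at 45 kg. At 60 kg or more there is no conflict, provided all limits apply together. The size rests on assumed weights, and the number of subjects affected cannot be estimated from the protocol. Sample size and the primary analysis are untouched. The point should be fixed because it concerns a safety ceiling and the consistent classification of deviations.

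**What to change.** The sponsor should reconcile the synopsis with all of section 6.2.3 (text, side limits, Table 17, its lead-in and its notes). The result should be one per-phase limit and one cumulative limit with a single time base, communicated to the sites. The lead-in should describe the table as maxima, and the closing sentence should name the limit it means. Which limit is right is for the sponsor to settle.

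If the reconciled limit depends on body mass, the protocol should also say which weight measurement applies. Weight is listed at Visit 1 (section 6.5.1) and RT1 (section 6.5.10). It is not scheduled at Visit 2 or Visit 3 (Table 1; sections 6.5.2 and 6.5.4), although Visits 1 and 2 may be combined. At RT2 it is in Table 3 but not in the procedure list of section 6.5.12.

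The reconciled limit should then be used when deviations are reviewed at the interim and final data review meetings.

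The cost is one protocol clarification and a site memo. Injected volume is already recorded by side, anatomical area and treatment (section 6.4.10), so the only data question is whether weight is taken at RT2.
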